### **12.2.3 Follow up of serious adverse events**

An SAE should be followed until it has resolved, has a stable sequelae, the Investigator determines that it is no longer clinically significant, or the subject is lost to follow up.

Information on SAEs obtained after clinical database lock will be captured through the Drug Safety database without limitation of time.

### **12.3 Immediate reporting of adverse events**

The following AEs must be reported immediately:

- SAE: AE that the Investigator classifies as serious by the above definitions regardless of causality
- Suspected transmission of an infectious agent via a medicinal product

- AEs of special interest as defined in [Section 12.1.2](#)

## 12.4 Anticipated serious adverse events

The following list of Anticipated SAEs has been identified, as these events are anticipated to occur in the population studied in this protocol at some frequency that is independent of drug exposure. This original list will remain in effect for the duration of the protocol. Note that listed events will not be regarded as anticipated SAEs if they are life threatening or if they result in the death of the study subject.

This list does not change the Investigator's obligation to report all SAEs (including Anticipated SAEs) as detailed in [Section 12.2.2](#).

**Table 12–1: Anticipated serious adverse events for the population of subjects with moderate to severe chronic plaque psoriasis**

MedDRA® system order class	MedDRA preferred term
Skin and subcutaneous tissue disorders	Any psoriatic condition HLT
Musculoskeletal and connective tissue disorders	Psoriatic arthropathy

HLT=high level term; MedDRA=Medical Dictionary for Regulatory Activities; SAE=serious adverse event

Note: Exception: Listed events will not be regarded as anticipated SAEs if they are life threatening or if they result in the death of the study subject.

## 12.5 Laboratory measurements

Clinical laboratory assessments consist of serum chemistry, hematology, and urinalysis. A centralized laboratory will be used to supply all laboratory test supplies and analyze all blood and urine samples for hematology, biochemistry and urinalysis measurements. Any unscheduled laboratory testing should also be collected using the central laboratory. Testing to rule out hepatitis B, hepatitis C, and HIV (see Exclusion Criterion #7, [Section 6.2](#)) will be performed at Screening in addition to those measurements listed in [Table 12–2](#).

Specific details regarding the handling and processing of serum chemistry, hematology, and urinalysis samples are provided in the study laboratory manuals.

**Table 12–2: Laboratory measurements**

Hematology	Chemistry	Urinalysis
Basophils	Calcium	Albumin
Eosinophils	Chloride	Bacteria
Lymphocytes	CRP	Crystals
Atypical lymphocytes	Magnesium	Glucose
Monocytes	Potassium	pH
Neutrophils	Sodium	RBC
Hematocrit	Glucose	WBC
Hemoglobin	BUN	Urine dipstick for pregnancy testing a

**Table 12–2: Laboratory measurements**

Hematology	Chemistry	Urinalysis
MCH	Creatinine	
MCHC	ALP	
MCV	AST	
Platelet count	ALT	
RBC count	GGT	
WBC count	Total bilirubin	
	LDH	
	Total cholesterol	
	Serum pregnancy testing a	

ALP=alkaline phosphatase; ALT=alanine aminotransferase; AST=aspartate aminotransferase; BUN=blood urea nitrogen; CRP=C-reactive protein; GGT=gamma glutamyltransferase; LDH=lactate dehydrogenase; MCH=mean corpuscular hemoglobin; MCHC=mean corpuscular hemoglobin concentration; MCV=mean corpuscular volume; RBC=red blood cell; WBC=white blood cell

a Pregnancy testing will consist of serum testing at the Screening and SFU Visits. The pregnancy test will be urine at all other visits.

Assessments of immunological variables are described in [Section 11](#). Assessments of PK and PD variables are described in [Section 10](#).

### 12.5.1 Evaluation of PDILI

The PDILI IMP discontinuation criteria for this study are provided in [Section 6.3.1](#), with the accompanying required follow-up investigation and monitoring detailed below. All PDILI events must be reported as an AE and reported to the study site and sponsor within 24 hours of learning of their occurrence. Any PDILI event that meets the criterion for potential Hy’s Law must be reported as an AESI (see [Section 12.1.2](#)), and, if applicable, also reported as an SAE (see [Section 12.2.1](#)).

Evaluation of PDILI consists of the diagnostic testing and continued monitoring included in [Table 12–3](#) (specific tests dependent on laboratory results and corresponding symptoms) and consultation with a local hepatologist (if applicable; discussed in [Section 12.5.1.1](#)). The local hepatologist is the expert usually consulted by the treating physician for assessment and management of potential hepatic disease. This would usually be a hepatologist, but may be a gastroenterologist. Additional investigation and monitoring may be required and adapted based on the diagnosis after the cause of the liver injury/abnormality is confirmed (details in [Section 12.5.1.5](#)).

The results of all monitoring, including laboratory testing and other testing, should be made available to the study site and Sponsor.

All initial tests resulting in abnormal hepatic laboratory values need to be repeated, but appropriate medical action must not be delayed waiting for the repeat result.

---

If tests are done locally for more rapid results, a concurrent sample should also be sent to the central laboratory whenever possible. Medical care decisions are to be made initially using the most rapidly available results and a conservative approach must be taken if the results from the 2 laboratory tests are significantly different. Data from the local and central laboratory are to be recorded on the applicable CRF pages.

When IMP is discontinued, all concomitant medications and herbal supplements that are not medically necessary should also be discontinued. In these cases, the investigator should also consider dose reduction for medically necessary concomitant medication and consider changing any medically required concomitant medication known to be hepatotoxic to a suitable alternative.

Rechallenge with a substance potentially causing drug-induced liver injury is dangerous, may be fatal, and must not occur.

Table 12–3 summarizes the approach to investigate PDILI.

REDACTED COPY  
This document cannot be used to support any marketing authorization application and any extensions or variations thereof.

**Table 12-3: Required investigations and follow up for PDILI**

Laboratory value		Symptoms a of hepatitis of hypersensitivity	Immediate		Follow up	
ALT or AST	Total bilirubin		Consultation requirements	Actions	Testing	Evaluation
≥3xULN	≥2xULN b	NA	Hepatology consult c Medical Monitor must be notified within 24 hours (eg, by laboratory alert) and subject discussed with Medical Monitor ASAP.	Immediate, permanent IMP discontinuation.	Essential. Must have repeat liver chemistry values and additional testing completed ASAP (see Section 12.5.1.4); recommended to occur at the site with HCP.	Monitoring of liver chemistry values at least twice per week until values normalize, stabilize, or return to within baseline values. d
≥3xULN	NA	Yes				
≥5xULN	NA	NA	Need for hepatology consult to be discussed. (required if ALT or AST ≥8xULN) Medical Monitor must be notified within 24 hours (eg, by laboratory alert) and subject discussed with Medical Monitor ASAP.	Immediate, permanent IMP discontinuation		

**Table 12-3: Required investigations and follow up for PDILI**

Laboratory value		Symptoms a of hepatitis of hypersensitivity	Immediate		Follow up	
ALT or AST	Total bilirubin		Consultation requirements	Actions	Testing	Evaluation

≥3xULN (and ≥2x baseline) and <5xULN (and ≥2x baseline)
	
<2xULN
	
No
	
Discussion with Medical Monitor required. Consider need for hepatology consult if there is no evidence of resolution (see Follow up requirements).c
	
Further investigation – immediate IMP discontinuation not required (see Section 12.5.1.2). IMP discontinuation required if any of the following occur:  
 
Subject cannot comply with monitoring schedule.
 
Liver chemistry values continue to increase
 
Liver chemistry values remain ≥3xULN (and ≥2x baseline) after 2 weeks of monitoring without evidence of resolution
 
 
	
Essential: Every attempt must be made to have repeat liver chemistry values and additional testing completed within 48 hours at the site with HCP (see Section 12.5.1.4).
	
Monitoring of liver chemistry values at least twice per week for 2 weeks.d
 
 
Immediate IMP discontinuation required if liver chemistry values continue to increase.
 
 
After 2 weeks of monitoring liver chemistry values:
 
 
Discontinue IMP if levels remain ≥3xULN (and ≥2x baseline) without evidence of resolutiond
 
 
Continue to monitor until values normalize, stabilize, or return to within baseline values.d

This document cannot be used to support any marketing authorisation application or variations thereof.

ALT=alanine aminotransferase; ASAP=as soon as possible; AST=aspartate aminotransferase; HCP=healthcare practitioner; IMP=investigational medicinal product; NA=not applicable; PDILI=potential drug-induced liver injury; ULN=upper limit of normal

a Hepatitis symptoms include fatigue, nausea, vomiting, and right upper quadrant pain or tenderness; hypersensitivity symptoms include eosinophilia (>5%), rash, and fever (without clear alternative cause).

b If the subject also has  $\geq 2 \times$ ULN ALP, the possibility of an indication of biliary obstruction should be discussed with the Medical Monitor.

c Details provided in [Section 12.5.1.1](#). The local hepatologist is the expert usually consulted by the treating physician for assessment and management of potential hepatic disease. This would usually be a hepatologist, but may be a gastroenterologist.

d Unless an alternative monitoring schedule is agreed by the investigator and UCB responsible physician. Determination of stabilization is at the discretion of the investigator in consultation with the hepatologist (as applicable) and UCB responsible physician, as needed.

### **12.5.1.1 Consultation with Medical Monitor and local hepatologist**

Potential drug-induced liver injury events require notification of the Medical Monitor within 24 hours (eg, by laboratory alert), and the subject must be discussed with the Medical Monitor as soon as possible. If required, the subject must also be discussed with the local hepatologist. The local hepatologist is the expert usually consulted by the treating physician for assessment and management of potential hepatic disease. This would usually be a hepatologist, but may be a gastroenterologist. If determined necessary, this discussion should be followed by a full hepatology assessment (see [Section 12.5.1.4](#)) and SAE report (if applicable).

### **12.5.1.2 Immediate action: determination of IMP discontinuation**

All PDILI events require immediate action, testing, and monitoring.

The immediate action is dependent on the laboratory values and symptoms of hepatitis or hypersensitivity and ranges from continuation of IMP (followed by immediate investigation) to immediate and permanent discontinuation (see [Section 6.3.1](#) and [Table 12-3](#) for details).

When IMP is discontinued, all concomitant medications and herbal supplements that are not medically necessary should also be discontinued. The investigator should also consider dose reduction for medically necessary concomitant medication and consider changing any medically required concomitant medication known to be hepatotoxic to a suitable alternative.

### **12.5.1.3 IMP restart/rechallenge**

Rechallenge with a substance potentially causing drug-induced liver injury is dangerous, may be fatal, and must not occur.

### **12.5.1.4 Testing: identification/exclusion of alternative etiology**

The measurements and additional information required for the assessment of PDILI events when there is a reasonable possibility that they may have been caused by the IMP are included but not limited to those listed in [Table 12-4](#) (laboratory measurements) and [Table 12-5](#) (additional information). Results of the laboratory measurements and information collected are to be submitted to the sponsor on the corresponding CRF. If the medical history of the subject indicates a requirement for other assessments not included below, these additional assessments should be completed and submitted, as applicable.

All blood samples should be stored, if possible. If tests are done locally for more rapid results, a concurrent sample must also be sent to the central laboratory.

The following measurements are to be assessed:

**Table 12–4: PDILI laboratory measurements**

Virology-related	Hepatitis A IgM antibody
	HBsAg
	Hepatitis E IgM antibody
	HBcAb-IgM
	Hepatitis C RNA
	Cytomegalovirus IgM antibody
	Epstein-Barr viral capsid antigen IgM antibody (if unavailable, obtain heterophile antibody or monospot testing)
Immunology	Anti-nuclear antibody (qualitative and quantitative)
	Anti-smooth muscle antibody (qualitative and quantitative)
	Type 1 anti-liver kidney microsomal antibodies (qualitative and/or quantitative)
Hematology	Eosinophil count
Urinalysis	Toxicology screen a
Chemistry	Amylase
	If total bilirubin $\geq 1.5 \times \text{ULN}$ , obtain fractionated bilirubin to obtain % direct bilirubin
	Serum CPK and LDH to evaluate possible muscle injury causing transaminase elevation
Additional	Prothrombin time/INR b
	Serum pregnancy test
	PK sample

ALT=alanine aminotransferase; CPK=creatine phosphokinase; HBcAb-IgM=hepatitis B core antibody-IgM; HBsAg=hepatitis B surface antigen; IgM=immunoglobulin M; INR=international normalized ratio; LDH=lactate dehydrogenase; PDILI=potential drug-induced liver injury; PK=pharmacokinetic; RNA=ribonucleic acid; ULN=upper limit of normal

a For detecting substances (ie, amphetamines, benzodiazepines, opioids, marijuana, cocaine, phencyclidine, and tricyclic antidepressants), additional tests may be performed based on the Investigator's medical judgment and patient's history.

b Measured only for subjects with ALT  $> 8 \times \text{ULN}$ , elevations in total bilirubin, and symptoms of hepatitis or hypersensitivity. Hepatitis symptoms include fatigue, nausea, vomiting, and right upper quadrant pain or tenderness; hypersensitivity symptoms include eosinophilia ( $> 5\%$ ), rash, and fever (without clear alternative cause).

The following additional information is to be collected:

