19. Subject has a history of uncompensated heart failure, fluid overload, or myocardial infarction, or evidence of new onset ischemic heart disease or in the opinion of the Investigator other serious cardiac disease, within 12 weeks prior to Baseline.
- 20a. Subject has >2x upper limit of normal (ULN) of any of the following: alanine aminotransferase (ALT), aspartate aminotransferase (AST), alkaline phosphatase (ALP), or >ULN total bilirubin ( $\geq 1.5 \times \text{ULN}$  total bilirubin if known Gilbert's syndrome). If subject has elevations only in total bilirubin that are >ULN and <1.5xULN, fractionate bilirubin to identify possible undiagnosed Gilbert's syndrome (ie, direct bilirubin <35%).

Tests that result in ALT, AST, or ALP up to 25% above the exclusion limit may be repeated once for confirmation during the Screening Period. Upon retesting, subjects whose ALT, AST, or ALP remain above the thresholds defined above, should not be randomized.

For randomized subjects with a baseline result >ULN for ALT, AST, ALP, or total bilirubin, a baseline diagnosis and/or the cause of any clinically meaningful elevation must be understood and recorded in the Case Report form (CRF).

If subject has >ULN ALT, AST, or ALP that does not meet the exclusion limit at screening, repeat the tests, if possible, prior to dosing to ensure there is no further ongoing clinically relevant increase. In case of a clinically relevant increase, inclusion of the subject must be discussed with the Medical Monitor.
21. Subjects with clinically significant laboratory abnormalities (eg, creatinine >1.5xULN, neutropenia <1.5x10^9/L, hemoglobin <8.5g/dL, lymphocytes <1.0 x10^9/L, platelets <100 x10^9/L). Individual screening tests for which the results are in error, borderline, or indeterminate for inclusion in the study, can be repeated once for confirmation during the screening period if they are within 25% of the exclusion limit. Upon retesting, subjects whose results remain outside this threshold should not be randomized.
22. Subjects with any other condition which, in the Investigator's judgement, would make the subject unsuitable for inclusion in the study.
23. Subjects have been exposed to more than 1 biological response modifier (limited to anti-TNF or IL-17-23) for psoriatic arthritis or psoriasis prior to the Baseline Visit. The list of prohibited medications is presented in [Section 7.8.2](#).

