### 6.3.1 Potential drug-induced liver injury IMP discontinuation criteria

Subjects with potential drug-induced liver injury (PDILI) must be assessed to determine if IMP must be discontinued. In addition, all concomitant medications and herbal supplements that are not medically necessary should also be discontinued.

The PDILI criteria below require immediate and permanent discontinuation of IMP:

- Subjects with either of the following:
  - ALT or AST  $\geq 5xULN$
  - ALT or AST  $\geq 3xULN$  and coexisting total bilirubin  $\geq 2xULN$
- Subjects with ALT or AST  $\geq 3xULN$  who exhibit temporally associated symptoms of hepatitis or hypersensitivity. Hepatitis symptoms include fatigue, nausea, vomiting, right upper quadrant pain or tenderness. Hypersensitivity symptoms include fever (without clear alternative cause), rash, or eosinophilia (ie,  $>5\%$ ).

The PDILI criterion below allows for subjects to continue on IMP at the discretion of the Investigator.

- Subjects with ALT or AST  $\geq 3xULN$  (and  $\geq 2x$  baseline) and  $< 5xULN$ , total bilirubin  $< 2xULN$ , and no eosinophilia (ie,  $\leq 5\%$ ), with no fever, rash, or symptoms of hepatitis (eg, fatigue, nausea, vomiting, right upper quadrant pain or tenderness).

Evaluation of PDILI must be initiated as described in [Section 12.5.1](#). If subjects are unable to comply with the applicable monitoring schedule, IMP must be discontinued immediately.

Investigators should attempt to obtain information on subjects in the case of IMP discontinuation to complete the final evaluation. Subjects with PDILI should not be withdrawn from the study until investigation and monitoring are complete. All results of these evaluations and observations, as well as the reason(s) for IMP discontinuation and subject withdrawal (if applicable), must be recorded in the source documents. The CRF must document the primary reason for IMP discontinuation.

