### **12.1.2 Adverse events of special interest**

An AE of special interest (AESI) is any AE that a regulatory authority has mandated be reported on an expedited basis, regardless of the seriousness, expectedness, or relatedness of the AE to the administration of a UCB product/compound.

Potential Hy's Law, defined as  $\geq 3 \times \text{ULN}$  ALT or AST with coexisting  $\geq 2 \times \text{ULN}$  total bilirubin in the absence of  $\geq 2 \times \text{ULN}$  ALP, with no alternative explanation for the biochemical abnormality, must ALWAYS be reported to UCB as an AESI (ie, without waiting for any additional etiologic investigations to have been concluded). Follow-up information should then be reported if an alternative etiology is identified during investigation and monitoring of the subject.

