**Table 12–5: PDILI information to be collected**

New or updated information
Concomitant prescription and over-the-counter medications (eg, acetaminophen, herbal remedies, vitamins); dosages and dates should be included.
Pertinent medical history, including the following: 
 
• History of liver disease (eg, autoimmune hepatitis, nonalcoholic steatohepatitis or other “fatty liver disease”)
 
• Adverse reactions to drugs
 
• Allergies
 
• Relevant family history or inheritable disorders (eg, Gilbert’s syndrome, alpha-1 antitrypsin deficiency)
 
• Recent travel
 

Progression of malignancy involving the liver (Note: Metastatic disease to the liver, by itself, should not be used as an explanation for significant AST and/or ALT elevations.)
The appearance or worsening of clinical symptoms of hepatitis or hypersensitivity (eg, fatigue, nausea, vomiting, right upper quadrant pain or tenderness, decreased appetite, abdominal pain, jaundice, fever, or rash)
Recent clinically significant hypotension or hypoxemia with compromised cardiopulmonary function
Alcohol and illicit drug use
Results of liver imaging or liver biopsy, if done
Results of any specialist or hepatology consult, if done
Any postmortem/pathology reports

ALT=alanine aminotransferase; AST=aspartate aminotransferase; PDILI=potential drug-induced liver injury

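### As worded, the protocol requires PT/INR in a liver-injury work-up only when ALT >8xULN, raised bilirubin and symptoms occur together; AST is left out, and this does not match the triggers in Table 12-3

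*Protocol*

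**What the plan says.** Protocol Section 12.5.1.4 sets out the measurements for assessing a PDILI event. It says they "are included but not limited to those listed in" Table 12-4 (laboratory tests) and Table 12-5 (other information). Table 12-4 includes prothrombin time/INR with a restriction in footnote b: "Measured only for subjects with ALT" >8xULN, "elevations in total bilirubin, and symptoms of hepatitis or hypersensitivity".

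The protocol's other liver triggers are built differently:

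- **Section 6.3.1** opens its stopping list with "The PDILI criteria below require immediate and permanent discontinuation of IMP". It then gives three conditions, each sufficient alone: ALT or AST >=5xULN; ALT or AST >=3xULN with total bilirubin >=2xULN; ALT or AST >=3xULN with symptoms.
- **Table 12-3** repeats these rows and makes the Section 12.5.1.4 testing essential. It calls for a hepatology consult in the bilirubin row. In the symptom row the consult cell is blank in the extracted text, and I read it as merged with the row above. In the >=5xULN row the consult is "required if ALT or AST ≥8xULN".
- **Section 12.1.2** defines potential Hy's Law as >=3xULN "ALT or AST with coexisting" bilirubin >=2xULN, without ALP >=2xULN and without another explanation. Symptoms play no part.
- **Table 12-5** collects "Results of any specialist or hepatology consult, if done".

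**The concern.** Footnote b decides what a mandatory work-up contains, and it can be read in two ways. The grammar (*only* together with *and*) makes the three conditions joint. The resemblance to Table 12-3's three consult triggers suggests that any one was meant to be enough, but the text does not say so.

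On the joint reading, the subjects with the most worrying laboratory pattern mostly fall outside the PT/INR requirement. A potential Hy's Law case without symptoms, or with ALT at or below 8xULN, has none. On the any-of reading that gap closes, but two mismatches with Table 12-3 remain. An AST-led rise is not counted, and a value of exactly 8xULN is missed because the footnote uses > where Table 12-3 uses >=.

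About 40 sites are planned (Section 5.1.3). Two subjects with the same pattern could therefore have different required panels, and on the literal reading PT/INR would depend on the site or the consulted hepatologist. The stake is the safety work-up of individual cases, not any trial-level inference.

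**Working it through.** The documents give no figure to reproduce, so the check is one of logic.

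**Rules compared.** Let M be the higher of ALT and AST, in multiples of ULN.

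- Literal footnote: ALT >8 and bilirubin >ULN and symptoms.
- Any-of footnote: ALT >8 or bilirubin >ULN or symptoms.
- Proposed: M >=8 or bilirubin >=2 or symptoms, within PDILI events.
- Consult required (Table 12-3): (M >=3 and bilirubin >=2) or (M >=3 and symptoms) or M >=8.
- Potential Hy's Law, enzyme and bilirubin part only: M >=3 and bilirubin >=2. ALP and alternative cause are not modelled.

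The footnote has no bilirubin cut-off, so >ULN is an assumption; the alternative is shown at the end.

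**Worked cases.** Table 12-3 requires a consult in all five. Cases 1 to 3 meet the enzyme and bilirubin part of potential Hy's Law.

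| Case | Literal | Any-of | Proposed |
|---|---|---|---|
| 1. ALT and AST 10x, bilirubin 3x, symptoms | yes | yes | yes |
| 2. As case 1, no symptoms | no | yes | yes |
| 3. ALT and AST 6x, bilirubin 3x, symptoms | no | yes | yes |
| 4. ALT 4x, AST 10x, normal bilirubin, no symptoms | no | no | yes |
| 5. ALT exactly 8x, AST 4x, normal bilirubin, no symptoms | no | no | yes |

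**Pattern count.** ALT and AST are each placed at <3, 3 to <5, 5 to <8, exactly 8, or >8xULN. Bilirubin is <=ULN, >ULN to <2xULN, or >=2xULN. Symptoms are absent or present. That gives 5 x 5 x 3 x 2 = 150 patterns.

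- *Potential Hy's Law.* 24 enzyme pairs have M >=3, so 24 x 1 x 2 = 48. Literal: 5 pairs with ALT >8, bilirubin >=2xULN, symptoms present = 5. Any-of and proposed: 48 each.
- *Consult required.* 24 pairs x 4 bilirubin/symptom cells = 96, plus 16 pairs with M >=8 x the 2 remaining cells = 32, total 128. Literal: 5 x 2 x 1 = 10. Any-of misses the 16 - 5 = 11 patterns with M >=8, ALT <=8, normal bilirubin and no symptoms, leaving 117. Proposed: 128.
- *Lowest tier of Table 12-3* (M 3 to <5, bilirubin <2xULN, no symptoms). 3 pairs x 2 = 6. Any-of requires PT/INR in the 3 with bilirubin above ULN; proposed in 0.
- *Permanent discontinuation.* 96 + 21 pairs with M >=5 x 2 = 138. Proposed covers 128. The 10 left have M 5 to <8, bilirubin <2xULN and no symptoms, where Table 12-3 also leaves the consult to discussion.

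**If the footnote's bilirubin item meant >=2xULN.** Literal becomes 5 of 48 and 5 of 128; any-of becomes 48 of 48 and 106 of 128.

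**The case against.** The strongest reply is that Table 12-3 sets consultation, stopping and monitoring rules and never says who should have PT/INR. Nothing obliges the two triggers to be equal, and keeping a test for a narrower group is a legitimate choice. Naming ALT alone might be deliberate: Table 12-4 also calls for CPK and LDH to look for a muscle source, and case 4 could be such a pattern. This stands in part. There are not two contradictory PT/INR rules, and intent cannot be settled from the text. But a deliberately narrow rule would hardly leave out most of the potential Hy's Law patterns that the protocol escalates everywhere else.

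Second, if the list means any of three, every potential Hy's Law pattern is covered. That is plausible. The AST-led and exactly-8xULN patterns are still missed, and a mild bilirubin rise in the lowest tier would then trigger the test.

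Third, the practical risk is largely handled. The test list is open-ended, the Medical Monitor must be notified within 24 hours, a potential Hy's Law case stops treatment permanently, the consult is mandatory and its results are collected. All true. But allowing a test is not requiring it, and the word *only* discourages it.

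Fourth, the counts are unweighted cells of a chosen grid. Seven of the 11 any-of misses have a highest enzyme value of exactly 8xULN, which is nearly a zero-width band. That is right; the counts show which patterns are left out, not how often they occur.

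**Conclusion.** The concern holds, as a minor drafting defect in a safety procedure. As worded, footnote b requires PT/INR in 5 of 48 potential Hy's Law patterns and 10 of 128 consult-required patterns. The any-of reading lifts this to 48 of 48 and 117 of 128, so neither reading matches Table 12-3 fully.

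This rests on reading the blank consult cell in Table 12-3's symptom row as merged with the row above, and on taking a bilirubin elevation in footnote b to mean >ULN; the alternative cut-off does not change the conclusion. The documents give no expected number of liver events, and it may be small. No analysis, discontinuation rule, Hy's Law definition or reporting step in the protocol or SAP depends on PT/INR.

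**What to change.** Replace the first sentence of footnote b to Table 12-4 so that PT/INR is measured when ALT or AST is >=8xULN, or total bilirubin is >=2xULN, or hepatitis or hypersensitivity symptoms are present. Keep the symptom definitions that follow.

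Table 12-4 applies to PDILI events, all of which have ALT or AST >=3xULN, so that condition need not be repeated. Taken outside that setting, the sentence would catch 4 of the 6 grid patterns with both enzymes <3xULN; opening it with a reference to PDILI events would remove any doubt. Within PDILI events it equals the consult rule in all 144 patterns (24 enzyme pairs x 6).

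The >=2xULN cut-off also keeps the test away from mild bilirubin rises in the lowest tier. That matters because exclusion criterion 20a sets the limit at >=1.5xULN "total bilirubin if known Gilbert's syndrome", so some subjects may enter with bilirubin above ULN.

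The cost is one sentence in a protocol amendment, a matching line in the laboratory manual, and one coagulation sample per additional qualifying event. PT/INR is already in the panel. Sample size, blinding, analysis, discontinuation and reporting are unaffected.
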